5.3 Statistical Methods for Efficacy Analyses

The analysis of the primary efficacy parameter, change from baseline in TFBUT at Day 35 (Visit 3) in the analysis eye will be based on a mixed model repeated measures (MMRM) analysis. MMRM is robust to data that are missing completely at random (MCAR) or missing at random (MAR).

The mixed model will include terms for baseline TFBUT (continuous), study treatment (SYSTANE BALANCE, REFRESH OPTIVE Advanced/ OPTIVE PLUS [UK]), visit (Day 15 [Visit 2], Day 35 [Visit 3]), and study treatment-by-visit interaction. For each subject, the error terms from all the visits represent the within-subject variability, and are assumed to follow a multivariate normal distribution with an unstructured covariance matrix. If the model first fails to converge using an unstructured (co)variance structure, then a hierarchical approach will be applied until a (co)variance structure is obtained where the model converges. Therefore the following (co)variance structures will be tested according to the pre-specified order: (1) unstructured (UN), (2) toeplitz (Toep), (3) autoregressive [AR(1)], (4) variance components (VC), (5) compound symmetry (CS). As soon as one model converges this will be the final model used, therefore no further testing of subsequent (co)variance structures will be required.

Within-group estimates of the mean change from baseline and the associated 95% CI in the analysis eye will be presented. Within-study treatment and estimates of the difference (SYSTANE BALANCE - REFRESH OPTIVE Advanced/ OPTIVE PLUS [UK]) in mean change from baseline in TFBUT between SYSTANE BALANCE and REFRESH OPTIVE Advanced/ OPTIVE PLUS (UK) and the associated 95% CI in the analysis eye will also be presented.

The assumptions of the above MMRM model will be evaluated using the Anderson-Darling Test and Normal-Probability plots. Homogeneity of variance between/ among study treatment groups will be evaluated visually. If the assumptions for MMRM are not met, further exploratory analyses will be performed, as necessary. If either assumption is clearly not met, then a non-parametric analysis will be performed for the analysis eye (e.g. an analysis of covariance [ANCOVA] model for change from baseline in TFBUT at Day 35 [Visit 3] with the terms baseline TFBUT and study treatment, but using ranked response and covariate variables).

Evidence of efficacy (non-inferiority) will be deemed established if the lower limit of the 95% CI (equivalent to the 1-sided 97.5% CI) for the adjusted estimate of the difference (SYSTANE BALANCE - REFRESH OPTIVE Advanced/ OPTIVE PLUS [UK]) is above - 1.0 second (non-inferiority margin). The non-inferiority margin was chosen as 1.0 second on the basis that an increase of at least 25% in the baseline TFBUT of a subject with lipid-deficient dry eye would be considered clinically meaningful since the subject would blink less often.

The analysis set for the primary efficacy assessment will be the PPS. As a sensitivity analysis, the analysis will be repeated for the FAS using the same model.

Observed values and change from baseline values for the analysis eye for the PPS and FAS will also be presented descriptively (N, mean, median, SD, standard error [SE], minimum, and maximum) at each study visit for each study treatment. A plot of mean change in TFBUT by study visit and study treatment with error bars representing +/- 1 SE will be presented using the analysis eye. The x-axis will be study visit and the y-axis will be the change in TFBUT from baseline.

Observed values from all visits for the RS will also be listed along with the following variables: treatment, investigator, subject, age, sex, race, ethnicity, visit, eye, baseline value, and value at the visit.

The analysis of the secondary efficacy parameters will also be based on a MMRM model. The mixed model will include terms for the respective baseline parameter value (continuous), study treatment (SYSTANE BALANCE, REFRESH OPTIVE Advanced/ OPTIVE PLUS [UK]), visit (Day 15 [Visit 2], Day 35 [Visit 3]), and study treatment-by-visit interaction. The same procedure as outlined for the primary efficacy analysis in selecting the best fitting covariance structure will be applied. Estimates of the difference in mean change from baseline between SYSTANE BALANCE and REFRESH OPTIVE Advanced/ OPTIVE PLUS (UK) and the associated 95% CIs in the analysis eye will be presented.

Each secondary endpoint will be evaluated for superiority of SYSTANE BALANCE over REFRESH OPTIVE Advanced/ OPTIVE PLUS (UK).

The analysis set for the secondary efficacy assessments will be the FAS. As a sensitivity analysis, the analysis will be repeated for the PPS using the same model.

Descriptive statistics and listings of the secondary efficacy parameters will also be provided. The same approach as outlined for the primary efficacy parameter will be applied.

Table 5–1 Summary of analysis strategy for primary and secondary efficacy endpoints

Endpoint	Main vs. Sensitivity Approach ^a	Test	Statistical Method ^b	Analysis Set	Missing Data Approach
Primary					
Change from baseline in TFBUT at Day 35 (Visit 3)	M	Non-inferiority	Linear mixed model ^c	PPS	Likelihood-based
Change from baseline in TFBUT at Day 35 (Visit 3)	S	Non-inferiority	Linear mixed model ^c	FAS	Likelihood-based
Secondary					
Change from baseline in TFBUT at Day 35 (Visit 3)	M	Superiority	Linear mixed model ^c	FAS	Likelihood-based
Change from baseline in TFBUT at Day 35 (Visit 3)	S	Superiority	Linear mixed model ^c	PPS	Likelihood-based
Change from baseline in Global Ocular Discomfort VAS score at Day 35 (Visit 3)	M	Superiority	Linear mixed model ^c	FAS	Likelihood-based
Change from baseline in Global Ocular Discomfort VAS score at Day 35 (Visit 3)	S	Superiority	Linear mixed model ^c	PPS	Likelihood-based
^a M=Main analysis approach; S=Sensitivity analysis approach					

Endpoint	Main vs. Sensitivity Approach ^a	Test	Statistical Method ^b	Analysis Set	Missing Data Approach
----------	--	------	---------------------------------	--------------	-----------------------

^bFurther details on statistical models are:
^cLinear mixed model with terms for baseline of the relevant endpoint, study treatment, visit and study treatment-by-visit interaction.

[REDACTED] The mixed model will include terms for the respective baseline parameter value (continuous) and study treatment (SYSTANE BALANCE, REFRESH OPTIVE Advanced/ OPTIVE PLUS [UK]). Estimates of the difference in mean change from baseline between SYSTANE BALANCE and REFRESH OPTIVE Advanced/ OPTIVE PLUS [UK] and the associated 95% CIs in the analysis eye will be presented. [REDACTED]

[REDACTED]
 The same approach as outlined for the primary and secondary efficacy parameters will be applied.

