8 SUBJECT POPULATION

The study population includes approximately 220 subjects to be randomized (200 evaluable subjects required) at approximately 10 sites. Up to 55 subjects may be recruited per site, and site recruitment targets may vary based on site capabilities, available patient population, and length of recruitment period. To participate in the study, subjects must be at least 18 years of age and exhibit dry eye symptoms. The expected duration of subject participation in the study is approximately 7 weeks (49 days); up to 2 weeks (14 days) during the run-in phase and 5 weeks (35 days) in the treatment phase. The complete inclusion and exclusion criteria are presented in Section 1.

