The Run-in Phase is open-label and all subjects will use Preservative-Free Saline eye drops for at least 7 days. The Treatment Phase is double-masked, with subjects randomized to receive either SYSTANE BALANCE or REFRESH OPTIVE Advanced for the duration of the 5 week treatment period. The Investigator, clinical site staff (except designated unmasked site personnel), Sponsor, and monitors involved in reporting, obtaining, and/or reviewing the clinical evaluations will not be aware of the specific masked study product being administered. This level of masking will be maintained throughout the conduct of the study. The randomization scheme will be generated and maintained by the Sponsor's (or designee) unmasked personnel who are not involved in the conduct or analysis of the study. Subjects will be assigned randomly to treatment groups via IRT with stratification by site. The sponsor study specific personnel will be masked throughout the course of the study. Once all study data have been validated and the database locked, individual subjects will be unmasked. In the event of a medical emergency where the knowledge of subject treatment is required, an individual Investigator will have the ability to unmask the treatment assignment for a specific subject.

Although this is a double-masked study, at least 1 designated person from each clinical site will be unmasked. This person will be responsible for dispensing, reclaiming, conducting inventory, and will be available to address any study product irregularities. This individual will also perform the instillation of masked study product at Visit 1 (Baseline), Visit 2 and Visit 3. Sites should make every effort to have the same unmasked observer throughout the study.

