11.4.1.2 Analysis Methods

The primary efficacy analysis population will be the PPS.

The analysis of the primary efficacy parameter, change from baseline in TFBUT at Day 35 in the study eye, will be based on a mixed model repeated measures (MMRM) analysis. The mixed model will include terms for baseline TFBUT, treatment (SYSTANE BALANCE,

REFRESH OPTIVE Advanced), visit (Day 15, Day 35), and treatment-by-visit interaction. The response variable is the change from baseline in TFBUT for the study eye.

An unstructured variance-covariance matrix will be used to model the within-subject correlation. If the unstructured variance-covariance matrix results in a lack of convergence then other covariance structures will be investigated.

Within-treatment and estimates of the difference (SYSTANE BALANCE – REFRESH OPTIVE Advanced) in mean change from baseline in TFBUT between SYSTANE BALANCE and REFRESH OPTIVE Advanced and associated 95% CI will be presented. Evidence of noninferiority will be deemed established if the lower limit of the 95% CI for the difference is above -1.0.

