11.4.2.2 Analysis Methods

The analysis of the secondary efficacy parameter LLT AUC₁₂₀ at Day 35, and change from baseline in Global Ocular Discomfort VAS score at Day 35, and change from baseline of the TFBUT at Day 35 will be based on a MMRM. The mixed model will include terms for baseline parameter values, treatment, visit (Day 15, Day 35), and treatment-by-visit interaction. Estimates of the difference in mean change from baseline between SYSTANE BALANCE and REFRESH OPTIVE Advanced and associated 95% CIs will be presented.

Each endpoint will be evaluated for superiority of SYSTANE BALANCE over REFRESH OPTIVE Advanced. The p-value from the one-sided test less than 0.025 for a difference in favor of SYSTANE BALANCE will indicate superiority of SYSTANE BALANCE over REFRESH OPTIVE Advanced.

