1.3 Randomization

The randomization scheme will be generated and maintained by the Sponsor’s (or designee) unmasked personnel who are not involved in the conduct or analysis of the study. Randomization will be implemented in an Interactive Response Technology (IRT) system. The randomization will be stratified by study site to ensure a balance of study treatment allocations within each investigational site. Randomization will be in a 1:1 ratio.

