12.1 SAS code

12.1.1 Mixed model repeated measures

This SAS code will be used for the MMRM analysis for the primary and relevant secondary endpoints.

```
proc mixed data=<analysis dataset>;  
class usubjid treatment visit;  
model <endpoint of interest>=<baseline of endpoint of interest> treatment  
visit treatment*visit/solution ddfm=kr;  
repeated visit / subject=usubjid type=un;  
lsmeans treatment*visit / pdiff=all cl alpha=0.05 slice=visit;  
run;
```

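### Randomisation is stratified by site, but no visible efficacy model includes site, so the interval that decides noninferiority may be wider than it needs to be

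*SAP*

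**What the plan says.** Site is the stratification factor in both documents. Protocol 9.4: "Subjects will be assigned randomly to treatment groups via IRT with stratification by site". SAP 1.3 adds the purpose: "The randomization will be stratified by study site to ensure a balance of study treatment allocations within each investigational site".

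None of the visible efficacy models contains site:

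- **Primary MMRM.** Protocol 11.4.1.2 begins its list with "The mixed model will include terms for baseline TFBUT, treatment (SYSTANE BALANCE" and goes on to the comparator, visit and treatment-by-visit. SAP 5.3 has the same terms: "The mixed model will include terms for baseline TFBUT (continuous), study treatment", then visit and the interaction.
- **Secondary MMRM.** Protocol 11.4.2.2: "The mixed model will include terms for baseline parameter values, treatment, visit (Day 15, Day 35), and treatment-by-visit interaction". SAP 5.3 and footnote c of Table 5-1 agree.
- **Non-parametric fallback.** SAP 5.3 gives as an example an ANCOVA "with the terms baseline TFBUT and study treatment, but using ranked response and covariate variables".
- **SAS code.** In SAP 12.1.1 the CLASS statement lists subject, treatment and visit. There is no RANDOM statement, so site does not enter as a random effect either.

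Centre and investigator appear only in listings. Region is a baseline summary and a subgroup factor (SAP 4.2 and 5.3.2), not a model term. The primary and secondary model text and the code's MODEL statement are not redacted, and no reason is given for leaving site out.

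**The concern.** Balancing the arms within each site takes most of any site difference out of the treatment comparison. A model without site does not use that balance: the site differences remain in the residual variance, and the model-based standard error overstates the true sampling error of the contrast. The primary decision compares a confidence limit with -1.0 s, so an inflated standard error bears directly on whether noninferiority is declared.

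The endpoint is a change score and the model adjusts for baseline, so a constant reading offset at one site is at least partly removed already. What matters is any site difference in TFBUT change that remains. Such differences are plausible but not shown. The trial runs in several countries, TFBUT is read by site investigators, and site sizes can vary widely: "Up to 55 subjects may be recruited per site, and site recruitment targets may vary based on site capabilities".

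At stake is precision on a primary test planned at about 80% power. The two superiority tests in the SAP omit site as well. Global Ocular Discomfort is subject-reported, so for that endpoint the argument is only that site is the stratification factor, and no size is claimed.

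**Working it through.** **Inputs from the documents** (Protocol 11.10, SAP 9): 200 evaluable subjects, 1:1, SD 2.5 s, margin 1.0 s, true difference 0, one-sided 0.025. About 10 sites (Protocol 1 and 8).

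**Assumptions.** The site share of variance, ρ, is not given; 0, 5, 10 and 20% are used with total SD held at 2.5 s. Ten sites is also an assumption, because the UK subjects in the SAP fall under a separate protocol that was not available. Site sizes and block size are assumed.

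**1. The plan's own figure.** With 100 per arm, SE = 2.5 × √(2/100) = 0.3536 s and the noncentrality is 1.0/0.3536 = 2.828. The noncentral t with 198 df gives 80.4% power, and 100 per arm is the smallest size reaching 80%. The stated 200 reproduces, as do the other five cells of the sample size table.

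**2. Planned half-width.** t(0.975; 198) × 0.3536 = 1.972 × 0.3536 = 0.697 s.

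**3. Effect of site.** With balance within site, the true standard error of the contrast is 2.5 × √(1−ρ) × √(4/200). The model without site still reports about 0.3536.

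- Power without site: Φ((1 − 0.697)/(0.3536√(1−ρ))).
- Half-width with site: t(0.975; 189) × 0.3536√(1−ρ), where 189 = 200 − 10 − 1.
- Power with site: noncentral t with 189 df.

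| ρ | Half-width without / with site (s) | Power without / with site | Change (points) | One-sided type I error without site |
|---|---|---|---|---|
| 0% | 0.697 / 0.697 | 80.4% / 80.3% | −0.1 | 0.025 |
| 5% | 0.697 / 0.680 | 81.0% / 82.3% | +1.3 | 0.022 |
| 10% | 0.697 / 0.662 | 81.7% / 84.3% | +2.6 | 0.020 |
| 20% | 0.697 / 0.624 | 83.1% / 88.2% | +5.1 | 0.014 |

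The type I error uses the t distribution: P(T₁₉₈ > 1.972/√(1−ρ)). The matching two-sided coverage of the planned interval is 95.0, 95.6, 96.1 and 97.1%.

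**4. Simulation with unequal sites.** Single visit, permuted blocks of 4 within site, least squares with and without fixed site effects.

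- *Sites of 6 to 50 subjects, total 200, 10,000 trials per setting.* At ρ = 5, 10 and 20% the half-widths without/with site are 0.694/0.680, 0.692/0.662 and 0.687/0.624 s. Power is 80.8/82.0, 81.9/84.0 and 83.7/88.3%. Type I error is 0.0238/0.0256, 0.0223/0.0268 and 0.0165/0.0253.
- *Sites of 3 to 55 subjects, 220 randomised, random exclusion to 200, 20,000 trials per setting.* At ρ = 0, 5, 10 and 20% power without/with site is 80.1/79.7, 81.8/82.7, 81.7/83.8 and 83.0/87.5%. Coverage without site is 94.8, 95.3, 95.6 and 96.5%.

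The simulated gains are slightly below those in the table. With only 10 sites, the residual variance of the model without site itself falls a little as ρ rises, so its half-width does not stay at exactly 0.697 s.

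**The case against.** The strongest reply is that nothing is broken. The omission is conservative, does not bias the estimate, and leaves planned power at 80% or more in every scenario. The stated purpose of stratifying is balance within site, which is achieved without a site term. All of this stands, and it rules out calling the point a validity problem.

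The size also depends on a variance that the documents do not give. Nothing in them supports the upper end of the range, and at 0% the site term costs a little power. That stands, and the gain is conditional.

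Third, the calculation is single-visit and has no baseline covariate. SD 2.5 s is stated for change from baseline, with no mention of covariate adjustment. If baseline explained an assumed 10 or 20% of the variance, power without site would already be about 84 or 88%, leaving less room for site to help. This is fair: the table shows the mechanism and an order of magnitude, not the exact behaviour of the MMRM.

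Finally, the rank-ANCOVA is only an example in the SAP, and changing the primary model after all subjects have exited is a heavier step than adding a sensitivity analysis. But SAP 11.1 records that the database was unlocked and the treatment code unbroken at Version 3.0, and the sponsor made a larger change (dropping the LLT analysis) at that point by amending the SAP alone. Keeping the protocol's model as a sensitivity analysis preserves the original result.

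**Conclusion.** The concern holds as a matter of efficiency and consistency. The trial randomises within site and then analyses as if it had not. If sites differ in TFBUT change, the planned interval is conservative. At assumed site shares of 5, 10 and 20%, including site narrows it by about 2.5, 5 and 10%. Power rises by about 1, 2 to 3, and 4.5 to 5 points, the lower figures coming from the simulations. At 0% there is essentially no gain or loss.

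No false claim of noninferiority becomes more likely under the planned model, and the sample size is not wrong. The sizes rest on an unknown between-site variance, an assumed 10 sites, assumed site and block sizes, and a single-visit calculation without the baseline covariate.

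**What to change.** Before unmasking:

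1. Add site as a fixed effect to the MMRM for TFBUT and Global Ocular Discomfort, in SAP 5.3, footnote c of Table 5-1 and the code in SAP 12.1.1. Add it to the rank-based fallback as well.
2. Write a rule for pooling very small sites within country, applied while treatment is still masked.
3. Keep the model without site as a prespecified sensitivity analysis, so the protocol-specified result is still reported.

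If the sponsor prefers to keep the protocol's model as primary, the minimum is a stated reason for omitting site and a prespecified site-adjusted sensitivity analysis.

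The cost is some SAP wording, one class variable, the pooling rule and about 9 degrees of freedom out of roughly 200. If sites do not differ, the loss is about 0.1 point of power with equal sites and about 0.4 point with very unequal, unpooled sites.

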2.4.2 Unscheduled visits

All data collected at unscheduled visits will be listed.

Adverse event (AE) and exposure to study treatment data collected at unscheduled visits will be used.

3 Analysis Sets

The **Screened Set (SCR)** will consist of all subjects who signed the informed consent form (ICF).

The **Randomized Set (RS)** will consist of all subjects who were randomized to one of the study treatment arms.

The **Full Analysis Set (FAS)** is used to describe the analysis set which is as complete as possible and as close as possible to the intent-to-treat (ITT) principle of including all randomized subjects. The FAS will include all randomized subjects who have at least 1 post-baseline primary endpoint (TFBUT) assessment.

The **Per Protocol Set (PPS)** will consist of FAS subjects who satisfy all inclusion/ exclusion criteria and who have no major PDs, which will be specified in the Deviations and Evaluability Plan (DEP).

The **Safety Analysis Set** will include all subjects exposed to post-randomization study product.

Evaluability for all subjects will be determined prior to breaking the code for masked study treatment assignment.

The primary and secondary efficacy analyses will be performed on both the FAS and PPS with the PPS providing the primary inference for the non-inferiority hypothesis and the FAS providing the primary inference for the superiority hypotheses.

Supportive analyses of the primary hypothesis will be conducted using the FAS. Similarly, supportive analyses of the secondary hypotheses will be conducted using the PPS.

The number of subjects excluded from the FAS and PPS and a listing of excluded subjects with reason for exclusion will be presented. Any inconsistencies in key study results between the FAS and PPS will be examined and discussed in the CSR.

All efficacy analyses will be according to randomized assignment (regardless of the study treatment they received).

Safety analyses will be conducted using the Safety Analysis Set on a treatment-emergent basis. The main safety analyses will focus on the investigational products (SYSTANE BALANCE, REFRESH OPTIVE Advanced/ OPTIVE PLUS [UK]). For treatment-emergent safety analyses, subjects will be categorized under the actual study treatment received.

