6.4 Interim Analysis for Safety

Not applicable.

7 Pharmacokinetic Analysis Strategy

Not applicable.

8 Analysis Strategy for Other Endpoints

Observed lipid layer thickness (LLT) values from all visits will be listed for the RS.

9 Sample Size and Power Calculations

This study will include approximately 220 randomized subjects in a 1:1 ratio of SYSTANE BALANCE to REFRESH OPTIVE Advanced/ OPTIVE PLUS [UK] to achieve 200 evaluable subjects. A total of 200 subjects will provide approximately 80% power to reject the null hypothesis of inferiority of mean change from baseline in TFBUT in the analysis eye at the 0.025 level of significance (1-sided), assuming a study treatment difference of 0.0, a SD of 2.5, and a non-inferiority margin of 1.0 seconds (NQuery, version 7.0).

Table 9-1 Sample size required to achieve 80% and 90% power with different assumed values of SD

Power	Assumed SD	Sample size (total evaluable)
80%	2.5	200
	2.75	240
	3.0	286
90%	2.5	266
	2.75	320
	3.0	382

10 References

Not applicable.

11 Revision History

The reason for the first amended (Version 2.0) Statistical Analysis Plan was to reflect Version 4.0 of the study protocol and Version 1.0 of the UK country specific study protocol and to add clarity to some of the study endpoints.

The reason for the second amended (Version 3.0) Statistical Analysis Plan is to reflect the change to protocol specified analyses (outlined in Section 11.1).

The current version of the Statistical Analysis Plan is based on the following: Version 4.0 of the study protocol and Version 1.0 of the UK country specific study protocol.

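### Noninferiority is decided on the per-protocol set alone; requiring the full analysis set to clear -1.0 s as well would be a cheap safeguard against response-related exclusions

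*SAP*

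**What the plan says.** The two documents agree with each other. Protocol 11.4.1.2 states "The primary efficacy analysis population will be the PPS", and SAP 5.3 states "The analysis set for the primary efficacy assessment will be the PPS". For the FAS, SAP 5.3 adds "As a sensitivity analysis, the analysis will be repeated for the FAS using the same model". Protocol 11.2 and SAP 3 assign primary inference to the PPS for noninferiority and to the FAS for superiority. SAP Table 5-1 marks the PPS row as the main noninferiority analysis and the FAS row as sensitivity.

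The success rule (SAP Executive Summary and 5.3) is one lower 95% confidence limit above -1.0 s. The same limit opens the Hochberg step in SAP 5.3.1.

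The PPS is the FAS minus subjects who fail an entry criterion or have a major deviation. Major deviations are listed in a separate Deviations and Evaluability Plan (DEP), which is not among the documents. SAP 3 contains three safeguards: evaluability is fixed before the code is broken, exclusions are counted and listed with reasons, and "Any inconsistencies in key study results between the FAS and PPS will be examined and discussed in the CSR".

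**The concern.** A major deviation after randomisation can be a consequence of how well the assigned drop works. Subjects must use the product as directed and avoid other artificial tears, and a subject who does poorly has a reason to breach either rule. If such deviations count as major and are more common on the test product, the PPS loses poor responders mainly from one arm and the difference shifts in favour of the test product. Masked evaluability review stops anyone from choosing exclusions by arm. It does not help when poor response itself produced the deviation.

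If the PPS then passes and the FAS does not, the plan declares noninferiority and opens the secondary tests. The disagreement is examined in the study report, but the decision stands. What is at stake is the 2.5% one-sided error rate for the primary claim.

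**Working it through.** **Inputs from SAP 9.** "A total of 200 subjects will provide approximately 80% power to reject the null hypothesis of inferiority"; "at the 0.025 level of significance (1-sided), assuming a study treatment difference of 0.0, a SD of 2.5"; "a non-inferiority margin of 1.0 seconds". Allocation is 1:1, with 220 randomised and 200 evaluable, an implied loss of 20/220 = 9.1%.

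**Reproducing the plan's figure.** n per arm = 2 × 2.5² × (1.960 + 0.842)² / 1.0² = 98.1, so 99 per arm and 198 in total by the normal formula. The noncentral-t version gives exactly 200, and it also reproduces the other five table entries (240, 286, 266, 320, 382). Power with 100 per arm is 80.7% (normal) or 80.4% (t). The sample size is not in error.

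**Bias of the PPS difference.** Let a share q of an arm be excluded for response-related reasons, with mean change lower by a gap g than in retained subjects. The retained mean then exceeds the whole-arm mean by q × g, so

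PPS difference - FAS difference = (q × g in the test arm) - (q × g in the control arm).

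This is zero when exclusions are uninformative (g = 0) or when the two products are equal.

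**False-noninferiority rate of the PPS-only rule at a true FAS difference of -1.0 s.** SE = 2.5 × √(4/200) = 0.354 s, and rate = P(Z > 1.96 - bias/SE). The q and g values are assumptions. Control exclusions are taken as uninformative.

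| Test-arm share q | Gap g | Bias q × g | Rate |
|---|---|---|---|
| 0 | any | 0 | 2.5% |
| 3% | 1.25 s | 0.0375 s | 3.2% |
| 3% | 2.5 s | 0.075 s | 4.0% |
| 9.1% (10 of 110) | 1.25 s | 0.114 s | 5.1% |
| 9.1% (10 of 110) | 2.5 s | 0.227 s | 9.4% |
| 10% | 1.25 s | 0.125 s | 5.4% |
| 10% | 2.5 s | 0.25 s | 10.5% |

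With the imbalance reversed the bias changes sign: at 10% and 2.5 s the rate is P(Z > 1.96 + 0.25/0.354) = 0.4%.

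A simulation of a two-sample t comparison at Day 35 (110 per arm in the FAS, 9.1% excluded per arm, gap 2.5 s in the test arm) gives 9.6% for the PPS-only rule. In 7.3% of trials the PPS passes and the FAS misses, against 0.7% at gap 0, so most of the false successes are of the kind the FAS would catch.

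**Requiring both sets.** With the PPS (200) nested in the FAS (220), the two test statistics correlate at √(200/220) = 0.953.
- Error at -1.0 s: 1.8% with uninformative exclusions and 2.0% to 2.5% across the table's scenarios.
- Power at a true difference of 0 ("assuming a study treatment difference of 0.0"): PPS alone 80.7%, FAS alone 84.3%, both 79.1%, a loss of about 1.7 points. The t-based simulation gives 80.3% and 78.6%, the same loss.

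These are single-visit approximations to the planned repeated-measures model. They assume that all 220 subjects have a post-baseline TFBUT.

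**The gate.** The FAS superiority test on TFBUT uses the same model and set as the FAS noninferiority check. A lower limit at or below -1.0 s cannot also be above 0. LLT is now only listed (SAP 11.1), which leaves the VAS. With TFBUT not rejected, SAP 5.3.1 requires a one-sided p below 0.025/2 = 0.0125 for the VAS.

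**The case against.** The choice of set is deliberate and stated consistently in both documents. Making the PPS primary for noninferiority is defensible, because dilution in the FAS can itself favour noninferiority. The FAS test is prespecified with the same model, exclusions are listed with reasons, and evaluability is settled under masking. All of this stands. It makes the point an improvement, not the correction of an error.

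The mechanism is also unproven. The DEP decides which deviations are major, and nothing shows they would be commoner on the test product; both products are lipid-based. Site staff instil the assigned drop before TFBUT at Visits 2 and 3, which may blunt the effect of poor home dosing. Subjects who add other tears may have better TFBUT, so excluding them need not remove low values. PPS exclusions also include entry-criterion failures, which arise before treatment. A 2.5 s gap is more than 60% of the roughly 4 s baseline mean in protocol 11.4.1.1 (2.5/4 = 62.5%). These arguments are fair, and they are why the size is given as a range that starts near 3%.

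A reader might infer three stronger things that the documents do not support:
- That the 2.5% level holds only if exclusions are unrelated to both outcome and arm. Outcome-related exclusions with equal effect in both arms cancel, and arm-related exclusions unrelated to outcome cause no bias.
- That an error rate near 10% is to be expected. That figure needs essentially the whole planned test-arm loss to be poor responders, with no such loss among controls.
- That a failed FAS would still open every superiority claim. Only the VAS is exposed.

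**Conclusion.** The point holds as a cheap improvement. The FAS has no binding role in the noninferiority decision, so a PPS pass with a FAS miss counts as success. The harm is conditional on exclusions that are both related to response and unbalanced against the test arm. On assumed values, the false-noninferiority rate is about 3-4% if 3% of the test arm is affected and about 5-10% if 10% is affected. It is 2.5% if exclusions are uninformative or balanced, and below 2.5% if the imbalance runs the other way. Without the DEP, the documents cannot place the trial within that range. The consequence for the secondary tests is limited to the VAS, at the stricter Hochberg threshold.

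**What to change.** Before unmasking, state in the SAP Executive Summary, 5.3 and 5.3.1: *Noninferiority is established only if the lower limit of the 95% CI is above -1.0 second in both the PPS and the FAS.* Open the Hochberg step on that condition, and relabel the FAS noninferiority row in Table 5-1 to match. Record the change in SAP 11.1 as a departure from protocol 11.4.1.2. SAP version 3.0 handled the LLT change in this way, when follow-up was complete but the database was unlocked and the code unbroken. No alpha adjustment is needed, because both sets must pass.

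The cost is SAP wording and about 1.7 points of power, so SAP 9 should state about 79% in place of about 80%.

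The change does not remove all selection. Subjects with no post-baseline TFBUT are in neither set, and protocol Table 2-1 calls for early-exit TFBUT only after at least 14 days of masked treatment.
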